### 2.4 Outcomes

The primary outcome assessing the effectiveness of delivery options is the proportion of patients accepting and completing 3HP treatment. Secondary outcomes are classified within RE-AIM domains and are described in full in the trial protocol.

## Primary Outcome

Outcome	Numerator	Denominator
Proportion accepting and completing 3HP treatment	Number who take at least 11 of 12 doses within 16 weeks from date of treatment initiation	Number randomized

## 2.5 Sample Size

We estimated our sample size for the primary outcome (N=1656; 552/arm) based on a minimum clinically important difference of 10% in 3HP completion, comparing patient choice vs. DOT arms. Of note, the Centers for Disease Control and Prevention (**CDC**) TBTC iAdhere study of 3HP delivery strategies chose a 15% non-inferiority margin between DOT and SAT based on cost-effectiveness modeling in the US. We chose 10% to be more conservative because similar modeling studies have not been done in low-income settings, and because ours is not a non-inferiority design. To be maximally conservative, we applied a Bonferroni correction based on two independent comparisons (choice vs. DOT and choice vs. SAT). Assuming a two-sided alpha of 0.025, and 5% loss between consent and allocation, a sample size of 552 participants per arm (N=1656 total) is required to provide power of 0.90 to detect this difference (Table 3). This sample size will also give us power of 0.85 to detect a point estimate of at least 80% effectiveness in the patient choice arm, assuming a true effectiveness of 85%. If the true effectiveness rises to 86%, our power to show effectiveness >80% increases to 0.96. Power was calculated using the PS - Power and Sample Size program.

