All interested participants who meet eligibility criteria and consent to be included in the study will be randomized via a computer-generated algorithm to one of three arms: facilitated DOT, facilitated SAT, and patient choice between facilitated DOT and facilitated SAT (with the help of a decision aid tool). Randomization will be performed using computer-generated random permuted blocks of variable size between 9, 12 and 15, with an equal allocation ratio between the three arms. Randomization numbers will be generated using a statistical software package and individual random assignment sheets will be placed and sealed in opaque envelopes in batches of multiple blocks to minimize predictability that would occur if single blocks were used. Generation of randomization numbers and their concealment will be done by a US-based Study Biostatistician who will not have contact with participants. The numbers will be passed on to the local Study Biostatistician for custody and onward transfer to Study Coordinator in numbers corresponding to the expected enrolments for given time periods. Accountability for released randomization number containing envelopes will be given prior to release of subsequent ones. Each eligible participant will be asked by a Study Coordinator or his/her designee to select an envelope which s/he will open to see the randomization number and study arm. This will help to avoid/mitigate participants from accusing the research team of selecting for them a study arm. All randomization numbers will be monitored daily by the Study Coordinator and weekly by the local Biostatistician and fortnightly by the US-based via a database at a data management center. Recruitment will be continued until 1656 participants are randomized and offered treatment (expected to be completed within 2 years).

Study Procedures (See Table 2 and Figure 1)***Day 1 (day of enrollment)***

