Sample size: We estimated our sample size for the primary outcome (N=1656; 552/arm) based on a minimum clinically important difference of 10% in 3HP completion, comparing patient choice vs. DOT arms. Of note, the Centers for Disease Control and Prevention (**CDC**) TBTC iAdhere study of 3HP delivery strategies chose a 15% non-inferiority margin between DOT and SAT based on cost-effectiveness modeling in the US.¹⁷ We chose 10% to be more conservative because similar modeling studies have not been done in low-income settings, and because ours is not a non-inferiority design. To be maximally conservative, we applied a Bonferroni correction based on two independent comparisons (choice vs. DOT and choice vs. SAT). Assuming a two-sided alpha of 0.025, and 10% loss between consent and allocation, a sample size of 552 participants per arm (N=1656 total) is required to provide power of 0.90 to detect this difference (Table 3). This sample size will also give us power of 0.85 to detect a point estimate of at least 80% effectiveness in the patient choice arm, assuming a true effectiveness of 85%. If the true effectiveness rises to 86%, our power to show effectiveness >80% increases to 0.96. We calculated power using a continuity-corrected chi-squared statistic (or Fisher's exact test) to evaluate the differences listed, assuming independent samples and a binomial distribution. Power was calculated using the PS - Power and Sample Size program (Dupont WD, Plummer WD: "Power and Sample Size Calculations: A Review and Computer Program", Controlled Clinical Trials 1990; 11:116-28).

Table 3. Power to detect 10% difference

Effectiveness	Power
---------------	-------

DOT	Choice	
70%	80%	0.90
75%	85%	0.94
80%	90%	0.98
85%	95%	0.998

2. Data Analysis:

Primary analyses will involve assessment of all listed primary (effectiveness of delivery options) and secondary (reach, effectiveness, adoption, and implementation) outcomes.

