### Power to detect 10% difference

Effectiveness		Power
DOT	Choice	
70%	80%	0.90
75%	85%	0.94
80%	90%	0.98
85%	95%	0.998

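### Protocol (10%) and SAP (5%) assume different pre-allocation losses for the same 552 per arm and the same power table; at the stated alpha the SAP's figure does not reproduce 552, and the table understates power by up to about 4 points

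*SAP*

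**What the plan says.** Both documents size the trial for a "minimum clinically important difference of 10% in 3HP completion, comparing patient choice vs. DOT arms", with a Bonferroni correction for two comparisons (choice against each of the other arms).

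- SAP 2.5 sets a two-sided alpha of 0.025 and continues with "5% loss between consent and allocation, a sample size of 552 participants per arm", a number that it says "is required to provide power of 0.90 to detect this difference".
- The protocol (Statistical Considerations, Sample size) has the same sentence, except for "10% loss between consent and allocation, a sample size of 552 participants per arm". It adds that power was computed with a continuity-corrected chi-squared statistic or Fisher's exact test.
- Both print the same table, headed in the SAP "Power to detect 10% difference". For DOT/choice rates of 70/80, 75/85, 80/90 and 85/95% the powers are 0.90, 0.94, 0.98 and 0.998.

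Three further provisions fix the analysed number. The protocol's Randomization section says "Recruitment will be continued until 1656 participants are randomized and offered treatment". The primary outcome tables (protocol Outcome Measures, SAP 2.4) use the number randomized as denominator. Protocol Data Analysis and SAP 3.5 keep participants who decline treatment after randomization in the primary analysis as non-completers.

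SAP 2.3 gives the SAP precedence over the protocol. The SAP's document history records no change to the loss figure.

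**The concern.** With alpha, power, effect and test held fixed, one required sample size cannot follow from both a 5% and a 10% loss. The loss is also placed before allocation, while the recruitment target and the primary denominator both count people already randomized. A pre-allocation loss therefore affects how many people must be consented. It removes nobody from the 552 per arm who are analysed, so a power table that nets it off describes a smaller trial than the one the recruitment rule delivers.

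What is at stake is the traceability of the main design figure. The sample-size justification will be reported with the results, the two documents disagree on one of its inputs, and the document that prevails does not reproduce its own number.

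**Working it through.** **Inputs.** p1 = 0.70 (DOT) and p2 = 0.80 (choice), from the first row of the table; d = 0.10; two-sided alpha 0.025, so z = 2.2414; power 0.90, so z = 1.2816; equal allocation (protocol, Randomization); continuity correction (protocol, Sample size).

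**1. Number needed per arm for 0.90 power.** With mean proportion 0.75:

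- √(2 × 0.75 × 0.25) = 0.6124 and √(0.70 × 0.30 + 0.80 × 0.20) = 0.6083
- Uncorrected: n0 = (2.2414 × 0.6124 + 1.2816 × 0.6083)² / 0.10² = 463.2, i.e. 464
- Corrected: n = (n0/4) × [1 + √(1 + 4/(n0 × d))]² = 115.8 × (1 + √1.0864)² = 482.95, i.e. 483

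**2. Inflating for loss, n/(1 − loss).**

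| Source | Loss | Corrected | Uncorrected | Stated |
|---|---|---|---|---|
| Protocol | 10% | 483/0.90 = 537 | 464/0.90 = 516 | 552 |
| SAP | 5% | 483/0.95 = 509 | 464/0.95 = 489 | 552 |

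The protocol's 10% comes within 3% of 552. The SAP's 5% falls about 8% short with the correction and 11% short without it.

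**3. Power at a given n.** Power = Φ{[(d − 1/n)√n − z × √(2 × mean × (1 − mean))] / √(p1(1 − p1) + p2(1 − p2))}. For n = 552 and 70/80%: (0.10 − 1/552) × √552 = 2.3069; 2.3069 − 2.2414 × 0.6124 = 0.9343; 0.9343/0.6083 = 1.536; Φ(1.536) = 0.938. All rows at alpha 0.025:

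| n per arm | Meaning | 70/80 | 75/85 | 80/90 | 85/95 |
|---|---|---|---|---|---|
| – | Printed | 0.90 | 0.94 | 0.98 | 0.998 |
| 483 | Needed for 0.90 | 0.900 | 0.942 | 0.979 | 0.998 |
| 497 | 552 less 10% | 0.909 | 0.949 | 0.982 | 0.998 |
| 524 | 552 less 5% | 0.924 | 0.959 | 0.987 | 0.999 |
| 552 | Randomized and analysed | 0.938 | 0.968 | 0.991 | 0.999 |

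Fisher's exact test at 552 gives nearly the same: 0.939, 0.969, 0.992 and 0.9997. Against the printed table, power at 552 is higher by 3.8, 2.8, 1.1 and 0.1 points.

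**4. Where the printed table may come from.** Two sets of inputs reproduce every printed digit.

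- Alpha 0.025 with 483 per arm: 0.900/0.942/0.979/0.998. This route does not lead to 552 under either loss figure (step 2).
- Alpha 0.05/3 with 524 per arm, which is 552 less the SAP's 5%: 0.900/0.944/0.981/0.998. The unrounded requirement at this alpha is 524.06, and 524.06/0.95 = 551.6, i.e. 552. Rounding up to 525 first gives 525/0.95 = 553, or 525 × 1.05 = 551.25, again 552.

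The second route recovers both the table and the sample size. A three-way correction also appears elsewhere in the protocol: the 98.3% interval for the 80% target. Neither document says that 0.05/3 was used for the comparisons, so this is an inference. At alpha 0.05/3 with all 552 analysed, power is 0.917/0.955/0.986/0.999, so the table would still be slightly low (at most 1.7 points).

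**The case against.** The strongest reply is that nothing is at risk. At alpha 0.025, power for 70% versus 80% is 0.909 even with 10% taken off, 0.924 with 5% off and 0.938 with none. So 552 per arm delivers at least 0.90 under either loss figure, and only the claim that 552 is required fails. The last two rows of the table move by about a point or less. The primary result will be a risk ratio with a 97.5% interval and Fisher's exact test (SAP 3.4), so a null finding would be judged from that interval rather than from planning power. The SAP also formally prevails, which settles which loss figure governs. All of this stands, and it limits the severity. It does not make 5% reproduce 552, and it does not make the table describe 552 analysed per arm.

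Two stronger readings are tempting. A reader might infer that the conflicting losses leave the trial short of power; the figures show the opposite. A reader might also infer that the table was certainly computed for 483 per arm. The documents do not support that, because 524 per arm at alpha 0.05/3 fits equally well and also yields 552.

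**Conclusion.** Wrong as written, minor severity. The two documents give different pre-allocation losses for one sample size, and at the stated alpha the SAP's 5% leads to 509 per arm, not 552. The trial as specified analyses 552 per arm, with power of 0.94/0.97/0.99/0.999 for a 10-point difference; the printed table understates this by up to about 4 points. The error is conservative. The comparison is not underpowered, and enrolment need not change. Whether the stated alpha of 0.025 is the one behind the table remains open.

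This rests on the continuity-corrected normal approximation (Fisher's exact test agrees closely), equal arms, and no one randomized being left out of the primary denominator. Withdrawal of consent after randomization is not explicitly addressed. The conclusion covers the between-arm comparison only, not the separate power statements for the 80% target.

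**What to change.** 1. Check the original calculation and record which alpha and which loss produced 552 and the table.
2. State one loss figure in both documents, and apply it to the number consented rather than to the 552 randomized.
3. State that 552 per arm are randomized and analysed. If the number needed for 0.90 power is kept, give it separately (about 483 per arm at alpha 0.025).
4. Reprint the power table at 552 per arm for the alpha the analysis uses. SAP 3.4 tests at 0.025, which gives 0.94/0.97/0.99/0.999. If three comparisons were intended, the row at 0.05/3 is 0.917/0.955/0.986/0.999, and the alpha in the text must change with it.

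The cost is a few sentences and one table in each document. With alpha kept at 0.025, enrolment, denominator, test and threshold all stay as they are.

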### 2.3 General comments

This statistical analysis plan covers all effectiveness, implementation, and cost-effectiveness/modelling outcomes. Trial results reporting will follow the CONSORT 2010 statement extension for randomized control trials.

This document summarizes effectiveness outcomes analysis for the primary outcome of the proportion of eligible participants who accept treatment and take at least 11 of 12 doses of RPT/INH within 16 weeks of treatment initiation and secondary outcomes for the implementation and cost-effectiveness of each delivery strategy. These endpoints will be evaluated through review of study documents and study registers for all patients enrolled in the 3HP Options Trial at Mulago ISS Clinic. This Statistical Analysis Plan is written in support of and is predominantly consistent with the full trial protocol version 1.4 (3HP\_Protocol\_Official\_v1.4\_12MAY2022); however, this analysis plan takes precedence.

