### 3.4 Primary analysis of primary outcome (intervention effect analysis)

Primary outcome analysis will include the comparing the proportion of those completing at least 11 of 12 doses within 16 weeks from date of treatment initiation for those in the DOT vs. SAT vs. choice arms. This will involve:

1. **Unadjusted intent-to-treat comparisons of effectiveness between arms:** Participants randomized to the choice arm will be treated separately from those randomized to either facilitated DOT or facilitated SAT; the proportion of those in the patient choice arm who choose DOT or SAT will be measured and reported, but the primary outcome will consider all individuals in this arm as randomized to patient choice. The primary outcome using ITT comparisons will be the unadjusted risk ratio and 97.5% two-sided confidence intervals (**CIs**), and Fisher's exact test to determine statistical significance (two-sided alpha of 0.025, including Bonferroni correction).
2. **Simple calculation (using the exact binomial CIs) of the effectiveness of each delivery option, with a target of 80%.** Whether 80% acceptance and completion is achieved will be based on the lower bound of the Bonferroni-corrected 97.5% CI exceeding 0.80 in any of the three arms. We will reject our null hypothesis if the lower bound of the 97.5% CI does not exceed 80%.

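### The stated power for the 80% target (0.85 and 0.96) is not the power of the planned Bonferroni-corrected exact-interval rule, which is about 0.79 and 0.93

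*SAP*

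**What the plan says.** The second primary hypothesis is that acceptance and completion of 3HP can exceed 80%. SAP 2.5 (Sample Size) gives its power in the choice arm: "power of 0.85 to detect a point estimate of at least 80% effectiveness in the patient choice arm, assuming a true effectiveness of 85" per cent. The Sample size paragraph of the protocol carries the same statement and, like the SAP, continues: "If the true effectiveness rises to 86%, our power to show effectiveness >80% increases to 0.96".

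The only method sentence for power is in the protocol. It names a "continuity-corrected chi-squared statistic (or Fisher's exact test) to evaluate the differences listed, assuming independent samples". That describes the two-sample comparisons in the power table, not a one-sample comparison with 80%.

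The decision rule is in SAP 3.4, item 2. The method is "Simple calculation (using the exact binomial CIs) of the effectiveness of each delivery option, with a target of 80" per cent, and the criterion is the "lower bound of the Bonferroni-corrected 97.5% CI exceeding 0.80 in any of the three arms". Item 1 of that section specifies the "unadjusted risk ratio and 97.5% two-sided confidence intervals" for the between-arm comparisons. The protocol's Data Analysis section has the same rule at 98.3%. On any difference from the protocol, SAP 2.3 says: "however, this analysis plan takes precedence". The denominator of the primary outcome is "Number randomized".

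**The concern.** A power statement should describe the rule that will be applied. Here the rule uses a corrected exact interval, but neither document gives the confidence level, sidedness or method behind 0.85 and 0.96. If those figures come from an uncorrected interval, they overstate the chance of success on a primary hypothesis, and a reader interpreting a missed target would rely on them.

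The wording adds to the doubt. It speaks of detecting a point estimate of at least 80%, whereas the rule requires the lower confidence limit to exceed 80%.

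**Working it through.** **Inputs**
- n = 552 in the choice arm (SAP 2.5). The allowance for loss (5% in the SAP, 10% in the protocol) applies between consent and allocation. Recruitment continues until 1656 are randomized (protocol, Randomization), and the denominator is the number randomized. So n is not reduced further.
- Target 0.80; true rates 0.85 and 0.86 (SAP 2.5).
- Exact binomial (Clopper-Pearson) interval at 97.5% (SAP 3.4) or 98.3% (protocol, Data Analysis).

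**Formulas**
- With tail area a on the lower side, the lower limit for x successes is the a-quantile of Beta(x, n − x + 1). It exceeds 0.80 exactly when P(X ≥ x | n, 0.80) < a.
- The critical count r is the smallest such x. Power at a true rate p is P(X ≥ r | n, p).

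**Step 1: reproduce the stated figures.** Take an uncorrected two-sided 95% interval, a = 0.025. The lower limit is 0.7996 at 460 and 0.8015 at 461, so r = 461 (type I error 0.0203). Power is 0.850 at 85% and 0.957 at 86%, which round to the stated 0.85 and 0.96.

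**Step 2: apply the SAP rule.** For a two-sided 97.5% interval, a = 0.025/2 = 0.0125. The lower limit is 0.7986 at 462 and 0.8005 at 463, so r = 463 (463/552 = 83.9%; type I error 0.0116). Power is 0.789 at 85% and 0.931 at 86%.

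**Step 3: other readings, all at n = 552**

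| Rule | Successes needed | Power at 85% | Power at 86% |
|---|---|---|---|
| Exact, two-sided 95% (no correction) | 461 | 0.850 | 0.957 |
| Exact, two-sided 97.5% (SAP) | 463 | 0.789 | 0.931 |
| Exact, two-sided 98.3% (protocol) | 465 | 0.716 | 0.894 |
| Exact, one-sided 97.5% | 461 | 0.850 | 0.957 |
| Exact, one-sided 98.3% | 462 | 0.821 | 0.945 |
| Normal, null variance, two-sided alpha 0.025 | – | 0.782 | 0.930 |
| Wald, two-sided alpha 0.025 | – | 0.853 | 0.966 |

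The Wald calculation comes close, but its second figure rounds to 0.97, and Wald is not the planned interval. An uncorrected 95% exact interval at n = 526 also comes close (0.853 and 0.957), but it too omits the correction. If the loss did reduce n, the SAP rule would do worse: 0.767 and 0.918 at n = 524, and 0.736 and 0.899 at n = 497.

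**Step 4: the literal wording.** A point estimate of at least 80% needs 0.80 × 552 = 441.6, so 442 successes. At a true 85% that has probability 0.999, so this is not what was computed.

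**Step 5: size of the gap.** The shortfall is 0.850 − 0.789 = 0.061 at 85% and, from the printed 0.96, 0.960 − 0.931 = 0.029 at 86%. With r = 463, power reaches 0.85 at a true rate of 85.35% and 0.96 at about 86.4%.

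**The case against.** The strongest objection is sidedness. Item 2 of SAP 3.4 does not say that its 97.5% interval is two-sided, the hypothesis has one direction, and only the lower limit is used. If a one-sided 97.5% bound was meant, 461 successes suffice and the printed figures are right. It could even count as a Bonferroni correction: starting from a one-sided 5% level, division by two gives a one-sided 97.5% bound. This reading cannot be excluded from item 2 alone. But item 1 of the same section calls its 97.5% intervals two-sided, and SAP 2.5 works with a two-sided alpha of 0.025, so two-sided is the more natural reading. The protocol's 98.3% rule misses the printed figures under either sidedness. If one-sided was intended, the SAP still has to say so.

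The second objection is that little depends on it. The cut-off moves by two participants in 552, the assumed true rates are round illustrations, and no sample size, analysis or estimate changes. The target may also be met in any arm: if all three arms were truly at 85% (an assumption), the chance that at least one succeeds under the SAP rule would be 1 − (1 − 0.789)³ = 0.99. All of this stands and limits the consequence. However, the documents state the power expressly for the choice arm, so the any-arm rule does not make the printed figure correct.

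**Conclusion.** The concern holds. Under the governing rule in SAP 3.4, the power for the 80% target in the choice arm is about 0.79 at a true 85% and 0.93 at 86%, against 0.85 and 0.96 stated: 6 and 3 percentage points lower. At a true 85%, the chance of a miss in that arm is about 21% rather than 15%. At the protocol's 98.3% level (two-sided), power would be 0.72 and 0.89, a gap of 13 and 7 points.

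This rests on a two-sided interval, the Clopper-Pearson method and 552 randomized. That the Bonferroni correction was left out of the power calculation is an inference from the match with the 95% interval; the mismatch with the two-sided rule does not depend on it. The point should be corrected because it is a power claim for a primary hypothesis, but it gives no reason to change the sample size.

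**What to change.** In SAP 2.5 and in the protocol's Sample size paragraph:
- Restate the power as about 0.79 at a true 85% and 0.93 at a true 86%, for a two-sided 97.5% exact binomial interval with 552 randomized. Use 0.72 and 0.89 only if the two-sided 98.3% level is kept.
- State the confidence level, sidedness, interval method and n behind the figures.
- Describe the event as the lower confidence bound exceeding 80%, not as detecting a point estimate of at least 80%.

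In SAP 3.4 item 2 and the protocol's Data Analysis section, settle on one level (97.5% or 98.3%) and say whether it is two-sided. If a one-sided 97.5% bound was intended throughout, saying so explicitly would let the present figures stand.

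The cost is a few sentences of text and, under the two-sided reading, less favourable power figures. No participants are added, and the analysis is unchanged if the two-sided 97.5% rule is confirmed.

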### Power to detect 10% difference

Effectiveness		Power
DOT	Choice	
70%	80%	0.90
75%	85%	0.94
80%	90%	0.98
85%	95%	0.998

